## **6.2 DETAILS OF DATA COLLECTION AT EACH VISIT/ PHONE CALL**

### **6.2.1 Inclusion (Incl. MV)**

During the inclusion consultation, the medical team will ask the patient to participate in this study. Written consent will be obtained; however if the patient refuses to participate in the study, the refusal with the corresponding reason, if available, will be documented in the study registry. The patient accepting to participate in the study will be randomised to receive or not a remote additional nurse-led follow-up during the follow-up period (randomisation ratio of 3:1).

The registration form must be completed and forwarded to Patientys by e-mail or FAX.

If the patient agrees to participate in the study, the investigator will collect the following data:

- Demographic information (age, gender, weight, height).
- NSCLC characteristics (date of first diagnosis, disease stage, performance status from the Eastern Cooperative Oncology Group [ECOG], biopsy date, type of mutation(s) detected, test/method used to assess mutation and previous treatments).
- Medical history, concomitant diseases, previous and concomitant treatment.
- Results of the complete physical examination: vital signs (heart and respiratory rate, blood pressure, temperature), and presence of any of the following symptoms: coetaneous, gastrointestinal, respiratory, ocular, cardiovascular and allergic.

As with any initiation of oral targeted therapy treatment, the medical team will counsel the patient on the oral targeted therapy, treatment schedule and precautions (lifestyle changes) to be taken in order to prevent treatment related adverse events, in addition to giving the patient a diary to report information related to the utilisation of healthcare services (telephone calls with or visits to their general practitioner or specialist, with any specialty).

During this consultation, and as per routine practice, the medical team will set the schedule of upcoming consultations. In this study, 3 data collection time-points at monthly intervals are defined (D30, D60, and D90). The frequency of visits should not be adjusted and the medical team should maintain his routine practice (example: if the investigator is used to see the patient on D15, the visit will still take place, but no information, except pharmacovigilance data, will be collected). As such, the data from the closest defined visit will be reported in the CRF.

The patient will also be asked to complete quality of life questionnaire (FACT Lung).

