| 
The study will take place over a period of 27 months. The recruitment phase will last approximately 24 months and each patient will participate for approximately 3 months.
 
At the inclusion visit (D0), the investigator will ask the patient whether he would like to participate in the study and will obtain his written consent. Refusal to participate including the reason if available will be collected in a register specific to this study (study register). The collected data will allow any selection bias to be identified.
 
Patients agreeing to participate will be randomised (3:1 ratio) and included in one of the following 2 groups:
 
 
• Group without 'remote additional personalised nurse-led follow-up': patients will receive the healthcare given routinely by their medical team (100 patients).
 
• Group with 'remote additional personalised nurse-led follow-up': patients will receive telephone calls from a nurse in addition to the healthcare given routinely by their medical team (300 patients).
 
 
All the patients will be seen according to normal practice by the study medical team. In this study, 3 data collection time points at monthly intervals are defined (D30, D60, D90); however, the frequency of visits should not be adjusted and the medical team should maintain his routine practice (example: if the investigator is used to see the patient on D15, the visit will still take place, but no information, except pharmacovigilance data, will be collected). As such, the data from the closest defined visit will be reported in the case report form (CRF) at each time-point.
 
The telephone calls will be made by a nurse from a company specialised in patients support called Patientys. Patients in the group with 'remote additional personalised nurse-led follow-up' will be contacted 8 times during the study (at D1, D7, D14, D21, D28, D44, D59 and D89). The nurse will make sure that the treatment takes place in good conditions; she cannot intervene in the medical care of the patient, nor give answer to the questions relative to the disease or to the treatment of the patient. The medical team remains the privileged contact of the patient.
 
During the first telephone call at D1, the nurse will confirm the enrolment of the patient in the study and will then inform the patient's general practitioner/pharmacist by letter or telephone call.
 
During the following telephone calls, the nurse will perform an evaluation with the help of a questionnaire and will collect treatment related AEs. After each telephone call, the nurse will establish a report. These reports will be sent to the investigators on the same day of the nurse follow-up phone call.
 
On arrival for the consultations (D0, D30, D60 et D90) with the investigator, the patient will be asked to complete questionnaires regarding treatment compliance, satisfaction and/or quality of life before the start of consultation, in the doctor's office or any other available private place.
 |   |                                 |                           |

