The nurse will also send, on the same day of follow-up phone call, all the information related to the SAEs, non-SAEs and any other PV information to the CRO in charge of data monitoring (copy of the AEs pages of the CRF sent to the investigators).

On arrival for the consultations with the investigator, the patient will be asked to complete questionnaires regarding treatment compliance, satisfaction and/or quality of life before the consultation, in the doctor's office or any other private place.

The CRO in charge of data monitoring will establish a hotline specifically for investigators and study personnel.

At Patientys centre, all incoming calls will be documented: during successful calls, an evaluation will be completed stating the date and time of the call. The failed calls will be documented in the study registry. No calls will be recorded.

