### **6.2.2 Other visits (MV1, MV2, MV3)**

At the 2nd and 3rd consultation visits (D30 and D60) during which data will be collected, the patient will be asked to:

- Complete the compliance questionnaire (Girerd).
- Complete the quality of life questionnaire (FACT Lung; only on D30).
- Bring their oral targeted therapy packets (empty or started) prescribed/consumed since the previous consultation visit.

- Bring their patient diary.

All the questionnaires will be completed before the start of consultations, in the doctor's office or any other available private place.

The medical team will record the number of tablets taken and not taken, and will report this information in the patient's CRF.

Adverse events and concomitant diseases and medications will be collected during these consultations. Data on the utilization of healthcare services (hospitalizations, emergency room visits, unscheduled consultation visits), including the number of visits and the number of calls to the general practitioner, will also be collected using the information reported by the patient in their patient diary.

During the last consultation visit (MV3 on D90), the patient will be asked to:

- Complete the compliance questionnaire (Girerd),
- Complete the quality of life questionnaire (FACT Lung),
- Complete the global satisfaction questionnaire,
- Bring their oral targeted therapy packets (empty or started) prescribed/consumed since the previous consultation visit,
- Bring their patient diary.

All the questionnaires will be completed before the start of consultations, in the doctor's office or any other available private place.

The medical team will record the number of tablets taken and not taken, and will report this information in the patient's CRF.

Adverse events and concomitant diseases and medications will be collected during these consultations. Data on the utilization of healthcare services will also be collected using the information reported by the patient in their patient diary.

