### **8.1 STUDY APPROVAL, PATIENT INFORMATION, AND INFORMED CONSENT**

This study will be initiated once all documents are reviewed by ethics committee (Comité de Protection des Personnes [CPP] Ile de France II) and other relevant health institutions concerned with studies of routine practice in accordance with applicable French legislation (Comité Consultatif sur le Traitement de l'Information en matière de Recherche dans le domaine de la santé [CCTRIS] / Commission Nationale de l'Informatique et des Libertés [CNIL], Conseil National de l'Ordre National des Médecins [CNOM]). Any substantial change to the protocol will be implemented only after receiving the approval of the CPP. Non-substantial changes will be informed to the CPP.

Patients participating in a routine practice study should be informed of the purpose of the study, duration, number of participants and their right to refuse participation in the study. Patients will be verbally informed by the medical team and will receive a copy of the patient information consent form (Appendix 10.1) which they must sign. This written consent must be obtained prior to initiation of any procedure related to the study.

The data collected during this study will be processed by computer. Treatment may be carried out in France or abroad, and will be conducted in compliance with the French law n° 78-17 of 6 January 1978 relating to computers, files and freedoms, as amended by Law 2004-801 of August 6, 2004. All necessary measures to ensure data confidentiality will be taken in accordance with the applicable legislation. Patients will not be identified by name or date of birth on the case report form or any other study document submitted to the sponsor or his representative. Patients will receive a unique identification number upon their consent to participate in the study. Patients should be informed that their medical records may be reviewed by staff appointed by the sponsor or his representative or by inspectors from the related authorities.

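### The protocol does not fix the D0 order of consent, baseline FACT-Lung and open envelope allocation, so the quality-of-life baseline may be collected after the group is known

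*Combined protocol and SAP*

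**What the plan says.** Four places bear on the order of events at D0.

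- **Section 6.2.1 (inclusion visit).** "During the inclusion consultation, the medical team will ask the patient to participate in this study. Written consent will be obtained". Next, "The patient accepting to participate in the study will be randomised to receive or not a remote additional nurse-led follow-up". The section goes on to the form for the call centre, the investigator's baseline data, counselling and the diary. It closes with "The patient will also be asked to complete quality of life questionnaire (FACT Lung").
- **Synopsis, Methodology.** "On arrival for the consultations (D0, D30, D60 et D90) with the investigator, the patient will be asked to complete questionnaires", and this is to happen "before the start of consultation, in the doctor's office or any other available private place". D0 is named. Section 3.1 has the patient "complete questionnaires regarding treatment compliance, satisfaction and/or quality of life before the consultation" but does not list the visit days.
- **Section 6.2.2 (MV1 to MV3 only).** "All the questionnaires will be completed before the start of consultations". Section 6.2.1 has no matching sentence for D0.
- **Section 8.1.** "This written consent must be obtained prior to initiation of any procedure related to the study".

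Tables 1 and 2 put randomisation and the quality-of-life questionnaire in the same D0 column without an order. FACT-Lung is the only questionnaire they schedule at D0, so the synopsis sentence can refer to nothing else at that visit. Section 7.1 describes the trial as open-label, and Section 7.5 allocates by envelope within each centre. Section 5.2.1 lists three FACT-Lung changes: D30 from D0, D90 from D30, and D90 from D0.

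**The concern.** FACT-Lung is self-reported and includes emotional and social well-being (Section 5.2.2). Once the envelope is opened, the team and the patient know whether the calls will come. The protocol's own reasoning makes a reaction plausible: the Introduction expects the calls to reassure patients, and Section 3.2 gives reducing refusals as one reason for the 3:1 ratio, which presumes that patients value the calls.

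If a patient answers the baseline questionnaire just after learning the group, the D0 score is no longer a pre-allocation measurement. Any reaction that differs between groups is then subtracted in the changes from D0 and appears as a group difference in the evolution of quality of life. Later analysis cannot recover the score that the patient would have given before allocation.

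**Working it through.** **Step 1. Can the passages be reconciled?**

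1. Synopsis: questionnaire first, then the D0 consultation.
2. Section 6.2.1: consent is sought within the D0 consultation, and only patients who accept are randomised.
3. Section 8.1: no study procedure before written consent.

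Items 1 and 2 together put FACT-Lung before consent, which item 3 forbids. The synopsis timing therefore cannot be followed literally at D0. Without it, two orders remain:

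- (a) consent, FACT-Lung, envelope;
- (b) consent, envelope, FACT-Lung.

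Neither breaches Section 6.2.1 or Section 8.1. Section 6.2.1 read from top to bottom suggests (b); the evident purpose of the synopsis suggests (a). Nothing workable requires (a). I could not see the graphic in Figure 1; its caption and key set no order.

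**Step 2. Which endpoints use D0?**

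Let x be the difference (nurse-led minus control) in mean D0 score caused only by knowing the group.

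| Change | Effect of x on the between-group difference |
|---|---|
| D30 - D0 | -x |
| D90 - D0 | -x |
| D90 - D30 | 0 |

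Two of the three changes are exposed, one-for-one and with opposite sign. With 36 items scored 0 to 4 (Section 5.2.2), a simple total runs from 0 to 36 × 4 = 144. If x were 1 to 3 points (an assumption, not a figure in the documents), the false difference would be 1 to 3 points in the opposite direction. The repeated-measures model in Section 7.3.3 is exposed in the same way if D0 enters it as a visit, because the shift would feed the group-by-visit interaction.

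**Step 3. What could that do to a test? Illustration only.**

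Inputs: 82 and 246 evaluable patients (Section 7.6); two-sided 5% test (Section 7.3); no true effect; every baseline exposed to the shift. The shift is written as b = |x| / SD of the change score, with b assumed because the documents give no FACT-Lung SD.

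Standard error in SD units: √(1/82 + 1/246) = 0.1275.

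Rejection rate: Φ(b/0.1275 - 1.96) + Φ(-b/0.1275 - 1.96).

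| b (assumed) | Rejection rate (nominal 5%) |
|---|---|
| 0.05 | 6.8% |
| 0.1 | 12.3% |
| 0.2 | 34.8% |
| 0.3 | 65.3% |

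These rates show sensitivity. They are not an estimate of what will happen. If only some sites follow order (b), the average shift is smaller in proportion.

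**The case against.** A reader might infer that the protocol prescribes allocation before the baseline questionnaire, that no other order is open to a site, and that every patient is therefore affected. The documents do not support this. Section 6.2.1 is a narrative without numbering or time words; FACT-Lung is added with an also, and the data list depends on the patient's agreement, not on allocation. The only explicit D0 timing, in the synopsis, points towards the questionnaire coming first. Consent, then FACT-Lung, then envelope is already permitted.

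A reader might also extend the point to ECOG status and symptoms recorded by the investigator. That does not follow either. Tables 1 and 2 list the physical examination and the disease characteristics (with ECOG) above the randomisation row, and row order sets no sequence in any case.

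Three further objections stand in part:

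- The size and direction of any shift are unknown.
- D30 and D90 answers are given with knowledge of the group whatever happens at D0, so fixing the order removes only one source of reporting bias.
- FACT-Lung change is one of more than 20 secondary endpoints.

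These objections limit the weight of the point. They do not remove it: the one sentence that would protect the baseline cannot be followed, and the operational section for the visit has no replacement.

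**Conclusion.** The point holds as an unresolved inconsistency with a concrete consequence. The synopsis, Section 6.2.1 and Section 8.1 do not yield one workable D0 order, so a baseline FACT-Lung completed after open allocation is possible, though not prescribed. If that happens and knowledge of the group moves the score by x between groups, the D30-D0 and D90-D0 comparisons are biased by -x and the D90-D30 comparison is not. The documents do not allow x, or the share of patients affected, to be estimated; the point values and rejection rates above rest on assumed shifts. Only secondary results are at stake. The primary endpoint, cumulated dose over three months, has no D0 baseline and is untouched. The change is still worth making because it is nearly free and a baseline taken after allocation cannot be restored later.

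**What to change.** - In Section 6.2.1, state one D0 order: written consent; FACT-Lung completed by the patient; then the envelope opened and the form sent to the call centre.
- Give the same order in the synopsis and in a note to Tables 1 and 2.
- Remove D0 from the synopsis sentence on completing questionnaires on arrival, and limit the general statement in Section 3.1 to the visits after inclusion.
- Add a CRF item confirming that the questionnaire was completed before the envelope was opened.

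The cost is a few sentences and one CRF check, with no added visit or assessment. At the visit, opening the envelope waits a few minutes while the patient completes the questionnaire.

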### **6.2.2 Other visits (MV1, MV2, MV3)**

At the 2nd and 3rd consultation visits (D30 and D60) during which data will be collected, the patient will be asked to:

- Complete the compliance questionnaire (Girerd).
- Complete the quality of life questionnaire (FACT Lung; only on D30).
- Bring their oral targeted therapy packets (empty or started) prescribed/consumed since the previous consultation visit.

- Bring their patient diary.

All the questionnaires will be completed before the start of consultations, in the doctor's office or any other available private place.

The medical team will record the number of tablets taken and not taken, and will report this information in the patient's CRF.

Adverse events and concomitant diseases and medications will be collected during these consultations. Data on the utilization of healthcare services (hospitalizations, emergency room visits, unscheduled consultation visits), including the number of visits and the number of calls to the general practitioner, will also be collected using the information reported by the patient in their patient diary.

During the last consultation visit (MV3 on D90), the patient will be asked to:

- Complete the compliance questionnaire (Girerd),
- Complete the quality of life questionnaire (FACT Lung),
- Complete the global satisfaction questionnaire,
- Bring their oral targeted therapy packets (empty or started) prescribed/consumed since the previous consultation visit,
- Bring their patient diary.

All the questionnaires will be completed before the start of consultations, in the doctor's office or any other available private place.

The medical team will record the number of tablets taken and not taken, and will report this information in the patient's CRF.

Adverse events and concomitant diseases and medications will be collected during these consultations. Data on the utilization of healthcare services will also be collected using the information reported by the patient in their patient diary.

Assessment of overall level of satisfaction of the general practitioner and the pharmacist will be collected via paper questionnaires that will be sent by Patientys along with a stamped return envelope to the address of the CRO responsible for the data monitoring of the study. The evaluation document of the overall level of satisfaction of the investigator of the medical team is given in the last page of the CRF and should ideally be completed at the last patient visit.

### 6.2.3      **Remote additional nurse-led follow-up**

This follow-up will be implemented only for patients in the 'with nurse-led follow-up' group. During each telephone call, the nurse will have to complete a pre-established questionnaire, an AE page, and a SAEs declaration form.

During the informed consent process, the patient may authorize a relative (i.e. a person he trusts and who can be among other, a family member, a friend or a housemate) to assist him

during the nurse-led phone call. The first and last name of this person will be specified on the informed consent form.

During the first telephone call (D1), nurses will confirm the registration of the patient. The name and contact details of the general practitioner and pharmacist of the patient will be collected in a study registry. These data will allow to inform the general practitioners and pharmacists of patients included in the ‘with remote additional personalised nurse-led follow-up’ group of the patient's participation in the study and to send them the global satisfaction questionnaire at the end of the study.

During subsequent telephone calls, the nurse will establish a ‘clinical evaluation’ using questions such as:

- “How are you feeling today?”
- “Did you take your medicine as your doctor has prescribed?”
- “Did you complete patient diary of the study?”

She will also collect AEs encountered during treatment intake. In particular, the following events will be collected:

- Gastrointestinal disorders (diarrhea, stomatitis, dyspepsia, cheilitis).
- Skin and subcutaneous tissue disorders (rash, acneiform dermatitis, pruritus, dry skin, the palmar-plantar syndrome).
- Infections (paronychia, cystitis).
- Appetite or metabolic disorders (decreased appetite, dehydration, hypokalemia).
- Nervous system disorders (dysgeusia).
- Eye disorders (conjunctivitis, dry eye, keratitis, tearing, light sensitivity).
- Respiratory disorders (epistaxis, rhinorrhea, interstitial lung disease, pneumonia, respiratory distress, allergic alveolitis).
- Musculoskeletal disorders (muscular spasms).
- General disorders (fever).
- Investigations (weight loss).
- Others.

The nurse will transmit to the investigator the telephone call report by e-mail or by FAX on the day of the follow-up phone call and will provide him with the AE page(s) of the CRF, if applicable. If needed the nurse may contact the medical team. Each AE will be recorded in the CRF and send to the CRO in charge of the data monitoring. The investigator of the team will also complete the AEs page of the CRF sent by the nurse by adding the intensity and the causal relationship with the oral targeted therapy.

- If case of serious adverse event (SAE), the investigator must complete and send the serious adverse event (SAE) form (SAE form) to the CRO in charge of data monitoring within 24h of the event. The causality will be determined by the investigator and recorded on SAE declaration form.
- In case of non-serious AE, the investigator should complete and send the AEs page of the CRF to the CRO in charge of data monitoring within 7 days of the event. The causality will be determined by the investigator and recorded on the AEs page of the CRF.

The nurse will also send, on the same day of follow-up phone call, the information related to the SAEs and non-SAEs to the CRO in charge of data monitoring.

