#### **2.2.2 Secondary objectives**

The secondary objectives are to evaluate:

- The impact of an additional nurse-led telephone follow-up on patient treatment compliance using Girerd questionnaire (Girerd 2001).
- To evaluate, during routine clinical practice, the impact of nurse-led telephone follow-up on overall patient treatment non-compliance with oral targeted therapy, following decision of the medical team (cumulated dose not taken\* during the 3-month follow-up).
- To evaluate, during routine clinical practice, the impact of nurse-led telephone follow-up on overall patient treatment non-compliance with oral targeted therapy, following decision of the patient (cumulated dose not taken\* during the 3-month follow-up).

*\* The cumulated dose (mg) of oral targeted therapy not taken between 2 visits is the sum of the doses (mg) of tablets not taken by the patient. The cumulated dose (mg) of oral targeted therapy not taken during the 3-month follow-up is the sum of the cumulated doses (mg) not taken between 2 visits during the 3-month follow-up.*

- Overall patient satisfaction with the level of care provided (Visual Analogue Scale [VAS]).
- Evolution of patient quality of life during the study (Functional Assessment of Cancer Therapy [FACT] Lung questionnaire; Cella, 1995).
- Use of healthcare such as emergency department visits/admissions, number and duration of unplanned hospitalisations, number of unplanned visits during the 3-month follow-up (visits to the investigator, to any other specialist or to the general practitioner).
- Overall satisfaction of the investigator (pneumologist/oncologist) and for the patients included in the group with a remote additional personalised nurse-led follow-up, the overall satisfaction of their pharmacist and general practitioner (VAS).
- Safety (data collected according to the Common Terminology Criteria for Adverse Events [CTCAE] version 4.03).
- Impact of the additional nurse-led follow-up on the frequency of calls to the general practitioners/specialists by the patient.

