The telephone calls will be made by a nurse from a company specialised in patients support called Patientys. Patients in the group with 'remote additional personalised nurse-led follow-up' will be contacted 8 times during the study (at D1, D7, D14, D21, D28, D44, D59 and D89, see Figure 1). The nurse will make sure that the treatment takes place in good conditions; she cannot intervene in the medical care of the patient, nor give answer to the questions relative to the disease or to the treatment of the patient. The medical team remains the privileged contact of the patient.

During the informed consent process, the patient may authorize a relative (i.e. a person he trusts and who can be among other, a family member, a friend or a housemate) to assist him during the nurse-led phone call. The first and last name of this person will be specified on the informed consent form.

During the first telephone call at D1, the nurse will confirm the enrolment of the patient in the study and will re-explain the calls schedule. Following this call, if the patient agrees to give the contact details of their physician and pharmacist, then the nurse will inform them, by letter or phone call, of the patient participation in the study.

During the following telephone calls, the nurse will perform a clinical evaluation by using a pre-established questionnaire and will collect treatment related AEs (see Section 6.2.3) as well as the pharmacovigilance (PV) information. After each telephone call, the nurse will establish a report.

The telephone call reports will be sent to the investigators on the same day of the nurse follow-up phone call.

The investigator will verify the severity of the AE and will determine the causal relationship with the oral targeted therapy.

- If case of serious adverse event (SAE), the investigator must complete and send immediately the serious adverse event (SAE) form (SAE form) to the CRO in charge of data monitoring (within 24h of the event). The causality will be determined by the investigator and recorded on SAE declaration form. In case of treatment exposure during pregnancy please refer to Section 5.3.2.2.
- In case of non-serious AE and/or of any other PV information, the investigator should complete and send the AEs page of the CRF to the CRO in charge of data monitoring within 7 days of the event. The causality will be determined by the investigator and recorded on the AEs page of the CRF.

[figure not shown]

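### Nurse calls prompt diary completion in one arm only, which puts the diary-based counts of GP and specialist visits and patient–GP calls at risk of differential recording

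*Combined protocol and SAP*

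**What the plan says.** **The diary.** At inclusion every patient, in either arm, receives "a diary to report information related to the utilisation of healthcare services (telephone calls with or visits to their general practitioner or specialist", of any specialty (section 6.2.1). Patients are asked to bring it to D30, D60 and D90. At D30 and D60, section 6.2.2 states that utilisation data, including visit counts and "the number of calls to the general practitioner, will also be collected using the information reported by the patient in their patient diary". For D90 it states: "Data on the utilization of healthcare services will also be collected using the information reported by the patient in their patient diary".

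**The nurse calls.** Section 6.2.3 says: "This follow-up will be implemented only for patients in the 'with nurse-led follow-up' group". Under section 3.1 these patients "will be contacted 8 times during the study", the first time at D1. For the calls after D1, section 6.2.3 gives sample questions, one of which is "Did you complete patient diary of the study".

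**The use made of the counts.** Section 2.2.2 names as a secondary objective the "Impact of the additional nurse-led follow-up on the frequency of calls to the general practitioners/specialists by the patient". Section 5.2.1 lists visit and call counts as secondary endpoints. Section 7.3.3 compares them between arms, and section 7.3 sets a two-sided 5% level. Section 7.4 plans missing-data handling for the primary endpoint only.

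**The concern.** The diary measures the outcome, and the intervention includes a reminder to fill it in. Randomisation does not protect against this, because the difference in recording arises after allocation. A contact that is not written down is also not seen as missing: it enters the analysis as a contact that did not happen.

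If the prompts work, nurse-arm diaries will be fuller and the recorded use in that arm will rise relative to control. A real fall in GP calls or visits could then be hidden, or an increase could appear where there is none. Reduced reliance on GPs and specialists is one of the effects the study sets out to examine, so the likely direction of the error works against its own objective.

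**Working it through.** **1. Trace of the text.**

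| Element | Nurse arm | Control arm | Section |
|---|---|---|---|
| Diary given at inclusion | Yes | Yes | 6.2.1 |
| Asked to bring diary at D30, D60, D90 | Yes | Yes | 6.2.2 |
| Diary used for utilisation counts | Yes | Yes | 6.2.2 |
| Diary question between visits | Up to 8 − 1 = 7 calls | None described | 3.1, 6.2.3 |
| Diary completeness reported by arm | Not described | Not described | – |

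**2. Which endpoints depend on the diary.** Section 6.2.1 defines its content as calls with, and visits to, the GP or a specialist. That covers about four endpoints: unplanned GP visits, unplanned visits to other specialists, and the two patient–GP call counts (one per direction).

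Section 6.2.2 also names hospital stays, emergency visits and unscheduled consultations. Hospitalisation, however, is a serious adverse event by definition (5.3.2.1) and is reportable within 24 hours in both arms (5.3.2.2). The medical team can know of visits to the investigator and of its own calls. No source is stated for calls between GP and medical team. The primary endpoint is a tablet count (5.1.2).

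**3. Effect on the rate ratio.** Let c_N and c_C be the proportions of true contacts recorded in the nurse and control arms. Then

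observed ratio = true ratio × c_N / c_C.

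| c_N / c_C | No true effect | True 20% reduction |
|---|---|---|
| 0.80 / 0.70 | 1.14 | 0.80 × 1.143 = 0.91 |
| 0.90 / 0.70 | 1.29 | 0.80 × 1.286 = 1.03 |

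**4. Effect on the test.** The documents give no recording or contact rates, so these are assumptions: 2 to 4 true contacts per patient, negative binomial with variance m + 0.7m², independent recording of each contact, and no true difference. The 82 and 246 patients are the evaluable numbers in section 7.6. Section 7.3.3 classes the counts as qualitative, for which section 7.3 offers Fisher's exact test. Wilcoxon applies if they are treated as quantitative. Simulated rejection rates at two-sided 5%:

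| Recording, nurse / control | Fisher, any vs none | Wilcoxon |
|---|---|---|
| 80% / 70% | about 7% | 11–14% |
| 90% / 70% | 13–16% | 30–41% |

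A repeat with 4,000 trials per scenario gave 7–8% and 15–18% for Fisher and 12–15% and 33–42% for Wilcoxon, so the entries are good to about three percentage points. With equal recording (80% in both arms) the same run gave 4–5% for both tests.

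*Hand check of the Fisher column at mean 2.* P(any recorded) = 1 − (1 + 0.7m)^(−1/0.7). With 90% recorded, m = 1.8 and P = 0.688. With 70% recorded, m = 1.4 and P = 0.623. The difference is 0.065. Its standard error is √(0.688×0.312/246 + 0.623×0.377/82) = 0.061, so z = 1.06. Rejection is about Φ(1.06 − 1.96) ≈ 0.18, and slightly less for the conservative exact test. Reducing the counts to any versus none shrinks a ratio of 1.29 to 0.688/0.623 = 1.10, which is why this test reacts less.

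**5. Rare events.** At an assumed 0.25 events per patient the rates are about 5–7% (80% vs 70%) and 11–12% (90% vs 70%). The repeat run gave 5–6% and 9–10%.

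**6. Masking.** With a true ratio of 0.80 and 2 or 4 contacts, Wilcoxon shows a significant reduction in 26–33% of simulated trials when 80% is recorded in both arms, 8–9% at 80% vs 70%, and 1–2% at 90% vs 70%.

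**The case against.** Several counter-arguments have weight.

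- **The question is only an example.** The final call questionnaire is not shown, so the number of prompts is unknown. This stands, and seven is an upper limit. But the questionnaire is described as fixed in advance, so the example indicates what is intended.
- **Controls are reminded too.** They receive the diary and are asked to bring it at three visits. This narrows the gap but does not close it, since nothing between visits is described for them.
- **The diary is not stated to be the only source.** This stands for hospital events, visits to the investigator and medical-team calls. A reader might infer that all ten or so utilisation endpoints are biased; sections 5.3.2, 6.2.1 and 6.2.2 do not support that. The serious-event route is not perfectly symmetric either, because the nurse also collects adverse events.
- **The planned tests are less sensitive than a rate-ratio test.** A log rate-ratio test under the same assumptions rejects in roughly 40–50% of trials at 90% vs 70%. The plan does not name that test, so the figure should not be quoted as its error rate.
- **Consequences are limited.** The endpoints are secondary, and the likely error works against claiming reduced use. Both are true, and they set the priority of the point. A masked benefit is still a wrong answer to a stated objective.

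**Conclusion.** The asymmetry is in the text, and a risk of differential recording follows from it. It bears mainly on GP visits, other-specialist visits and patient–GP calls. The most likely direction is over-counting in the nurse arm.

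A reader might go further and say these comparisons are biased by a known amount. The documents do not support that: they give no recording rates, no contact rates and no final call script. The ratios of 1.14 and 1.29 and the rejection rates above illustrate what a 10- or 20-point gap in recording would do under the assumed contact rates and dispersion. They do not forecast the gap. If the prompts left recording unchanged, there would be no bias.

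The point calls for a cheap improvement and does not threaten the primary result.

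**What to change.** 1. Remove the diary question from the nurse's call questionnaire. It serves data collection, so the supportive content of the calls is unchanged.
2. At D30, D60 and D90, have the medical team check the diary for gaps with every patient, using the same procedure in both arms. Patients already bring the diary to these visits; the explicit check is new.
3. Take hospitalisations, emergency admissions at the site and visits to the investigator from site records where available.
4. Report diary return and completeness by arm, and read the diary-based comparisons in that light.

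The cost is a change of script and a few minutes at visits that already take place. Nurse-arm diaries may become slightly less complete. Some asymmetry may remain, because the calls can themselves act as reminders; item 4 would help to show it.
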